Objectives:	
Principal aim: SAFETY
 
The primary objective of the study is to confirm the safety of a marketed auricular spray with reverse and microdiffusion nozzle by clinical examination by ENT specialist and by the scoring of the irritation of the ear canal at D60 in comparison with basal scoring of irritation at D0 (scale 0 to 3) such as:
 
 
- 0: no irritation,
 
- 1: slight irritation (located slight erythema and/or dryness),
 
- 2: moderate irritation (clear erythema or dryness which may be visible on the whole treated area),
 
- 3: severe irritation (serious erythema with potential oedema and/or scar).
 
 
Potential adverse events collection.
 
Secondary aims: EFFICACY/PERFORMANCE PREVENTION for investigational device with reverse nozzle, investigational device with microdiffusion nozzle and for control group, in comparison to the baseline (D0) and between groups:
 
 
• scoring of the obstruction of ear canal by the Investigator
 
 
0: no obstruction – normal and/or no significant presence of cerumen in the ear canal. The membrane is clearly visible.
 
1: <25% minimal, very little and mostly insignificant impacted cerumen. The tympanic membrane is visible, but with still a little bit cerumen.
 
2: 25-50% mild, some excessive impacted cerumen causing partial occlusion of the ear canal. The tympanic membrane is not entirely visible, quite difficult to see.
 
3: 50-75% moderate, moderate and excessive impacted cerumen causing partial occlusion of the ear canal. Partial to very little of the tympanic membrane is visible.
 
4: 75-100% severe, severe and excessive impacted cerumen causing partial or complete occlusion of the ear canal. Little if any of the tympanic membrane is visible.
 
 
• audiogram with classification of the loss or gain hearing function using the following scale (only for subjects more than 6):
 

YSLAB	Medical Device CIP #23E1670	Final version 2.0 Date: 09/11/2023	Confidential Page 11/64
-------	--------------------------------	---------------------------------------	----------------------------

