	
No hearing function loss, hearing function loss between 5 to 10dB, hearing function >10dB (Subha et al.2006), hearing function win between 5 to 10 dB, hearing function win >10dB.
 
Additionally, the secondary objective of this study will be to see if the investigational device is more efficient in children, adults or elderly subjects (for both nozzles - reverse or microdiffusion).
 
 
• Subject's self-evaluation using a questionnaire.
 
• Evaluation of the effect on the number of auricular affection (such as otitis) during the use period (daily log).
 

Design:	Open study, randomized, before / after treatment, with tested product versus control group, in parallel groups
Planned Sample Size:	
99 included subjects and results delivered on 90 subjects.
 
 
• 1 group of 72 included subjects in order to have results on 66 subjects (33 subjects using product with the "reverse diffuser" and 33 using the product with the "microdiffusion diffuser")
 
• 1 group of 27 included subjects in order to have results on 24 subjects not using a spray (control group). (in case of discomfort or pain, they are allowed to use ear drops prescribed by a doctor after a medical examination)
 

Number of investigational study sites:	2 centers
Inclusion criteria:	
 
1. Gender: female and/or male.
 
2. Age: 
 
- 30 to 40% having age between 3 to 12 yo,
 
- 30 to 40% between 13 to 65 yo,
 
- 30 to 40% more than 65 yo.
 
 
 
3. Subjects able to use the tested product.
 
4. Subjects having history of cerumen occlusion more than once a year with or without symptoms (reduction of hearing function, obstruction feeling of the ear canal,..).
 
5. Subjects having ear help system or regular users of systems such as anti-noise plugs or headsets (only for the 13yo subjects and more).
 
6. Subjects having a clinical score of ear canal obstruction of 2 or 3 at D0.
 

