Statistical methods:	
The analysis of the primary endpoint will be performed on the ITT and population.
 
The analysis of the secondary endpoint will be performed on the population.
 
The analysis of the safety/tolerance parameters will be performed on "safety" population.
 
Primary endpoint:
 
The irritation is assessed by the Laryngologist using a 4-point structured scale (from "No irritation (0)" to "Severe irritation (3)" on D0 and D90).
 
For each product, a paired t-test will be used to test whether the change from baseline (D90-D0) differ significantly from 0. The normality assumption will be checked using a Shapiro-Wilk test (<math>\alpha=0.01</math>), in case of rejection, a Wilcoxon signed ranks test will be used.
 
To test whether the products differ statistically in terms of change from baseline (D90-D0), a two-sided t-test is used. If the normality assumption is not met, a non-parametric approach is used with a Wilcoxon signed rank test.
 
Secondary endpoints:
 
For each secondary parameter:
 
 
• Clinical score of the irritation with structured scale
 
• Clinical score of the obstruction of ear canal
 
• Results of audiogram with classification of the loss or win hearing function.
 
• The number of auricular affection (such as otitis) during the use period
 
 
For each product, a paired t-test will be used to test whether the change from baseline (D90-D0) differ significantly from 0. The normality assumption will be checked using a Shapiro-Wilk test

YSLAB	Medical Device CIP #23E1670	Final version 2.0 Date: 09/11/2023	Confidential Page 13/64
-------	--------------------------------	---------------------------------------	----------------------------

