## FLOW-CHART

Procedure (time-points)	V1	V2
Intervals	D0	D90 (+/-3)
Informed Consent	●	
Medical exam	●	
Medical background and previous treatment	●	
Clinical scoring including irritation of the ear canal	●	●
Audiogram	●	●
Dispense product and daily log	●	
Collect product and daily log		●
Subjective evaluation questionnaire		●
Adherence control, record of AE, concomitant treatments	●	●
End of study form		●

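### The D90 irritation and obstruction scores are clinician visual grades in an open study, and nothing in the supplied pages keeps the scorer from knowing the group

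*Combined protocol and SAP*

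**What the plan says.** The Design row of the synopsis reads "Open study, randomized, before / after treatment, with tested product versus control group, in parallel groups". The Planned Sample Size row gives 33 subjects with results per nozzle and 24 controls who use no spray. No sham is described, so subjects necessarily know whether they are spraying.

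For the primary endpoint, Statistical methods states that "The irritation is assessed by the Laryngologist using a 4-point structured scale", at D0 and D90. The anchors are descriptive; grade 1, for example, is defined as "slight irritation (located slight erythema and/or dryness" (closing bracket omitted). The secondary aims include "scoring of the obstruction of ear canal by the Investigator", on a 0 to 4 scale. The Objectives row puts the purpose this way: "The primary objective of the study is to confirm the safety of a marketed auricular spray".

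In the flow-chart, "Clinical scoring including irritation of the ear canal" is marked at both visits. "Collect product and daily log" is marked at D90, and "Adherence control, record of AE, concomitant treatments" at both visits. No row or note separates the scorer from these tasks or puts them in order.

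The Objectives row names D60 for irritation, whereas Statistical methods and the flow-chart use D90. I follow D90 here.

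**The concern.** An open study for subjects does not require an open scorer. A returned spray can, a use log or a conversation about adherence tells the specialist which group the subject is in. If any of these comes before the grade is written down, the grade is given with that knowledge. The scales leave room for judgement: slight versus clear erythema helps separate irritation grades 1 and 2, and the obstruction bands share their limits at 50% and 75%.

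The primary aim is to confirm safety, and the test asks whether the change differs from zero. Under-scoring of irritation in spray users would make a reassuring result easier to reach. Closer scrutiny of known spray users would do the opposite and could produce a false signal. Nothing in the planned analysis (t-tests or Wilcoxon tests on D90 minus D0) can detect or remove either error.

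**Working it through.** **The plan's own figures.** The counts add up: 33 + 33 + 24 = 90 with results and 72 + 27 = 99 included. The supplied pages give no effect size, SD, power or margin, so the sample size cannot be rebuilt from a power formula. The effect of a scoring bias cannot be derived from the documents either. What follows is an illustration.

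**Inputs from the documents.** One spray arm of 33, control group of 24, two-sided 5% tests, endpoint D90 minus D0.

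**Inputs assumed.** SD of the change 0.4 to 0.8 grade; average under-scoring b in spray users of 0 to 0.3 grade; for the power calculation, a true increase of 0.4 grade in spray users relative to control.

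**Formulas (normal approximation).**
- Between groups: SE = SD × √(1/33 + 1/24). With SD 0.6, SE = 0.6 × 0.268 = 0.161.
- Power to see the harm: Φ((0.4 − b)/SE − 1.96).
- False-positive rate with no true difference and a shift b in either direction: 1 − Φ(1.96 − b/SE) + Φ(−1.96 − b/SE).

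**Power to see a true +0.4 grade, 33 v 24.** For SD 0.6 and b = 0: Φ(0.4/0.161 − 1.96) = Φ(0.52) = 70%. For b = 0.1: Φ(0.3/0.161 − 1.96) = Φ(−0.10) = 46%.

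| SD | b = 0 | 0.1 | 0.2 | 0.3 |
|---|---|---|---|---|
| 0.4 | 96% | 80% | 46% | 15% |
| 0.6 | 70% | 46% | 24% | 9% |
| 0.8 | 46% | 29% | 15% | 7% |

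**False-positive rate, 33 v 24, shift in either direction (nominal 5%).**

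| SD | 0.1 | 0.2 | 0.3 |
|---|---|---|---|
| 0.4 | 15% | 46% | 80% |
| 0.6 | 10% | 24% | 46% |
| 0.8 | 8% | 15% | 29% |

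**Before/after test in one spray arm (n = 33, SD 0.6).** SE = 0.6/√33 = 0.104. The same shifts give false-positive rates of 16%, 48% and 82%.

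**The floor of the irritation scale.** A grade of 0 cannot be scored lower, so under-scoring acts only on subjects at grade 1 or above. An average of 0.1 grade over 33 users is 3.3 one-grade reductions and needs at least 10% of users at grade 1 or above. In the illustration, if the +0.4 came from one-grade rises in 40% of users (0.4 × 33 = about 13), under-scoring by 0.1 means misgrading a quarter of them (3.3/13.2), and by 0.2 a half.

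If irritation is rare, the average shift is far smaller. With 3 of 33 users irritated (9.1%) and 10% of those misgraded, it is 0.10 × 3/33 = 0.009 grade.

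**Check on a 4-point score.** A rank-sum simulation (33 v 24) assumed 70% at grade 0 and shifted 30% of spray users by one grade at D90, with no true difference. It rejected in 19% of trials when scores were shifted up and 6% when shifted down. When most scores are 0, the more visible error is a false signal from over-scoring. Under-scoring does its damage by hiding irritation that is really there.

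**The case against.** A reader might infer more than the documents support, in four ways.

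- **A known direction favouring the device.** The documents do not say how expectation would act on irritation. A specialist asked to look for irritation may look harder in known spray users and score up. A likely direction, in favour of the spray, can be argued only for obstruction, which is one of four unranked secondary endpoints. This objection stands.
- **A fixed shift of 0.1 or 0.2 grade on irritation.** The floor at grade 0 and the absence of any stated irritation rate rule this out as an estimate. The shifts above are assumptions. This also stands.
- **A biased baseline.** Inclusion criterion 6 requires a D0 obstruction score of 2 or 3, and exclusion criterion 4 rules out a score of 4. D0 obstruction is therefore probably scored before allocation, and irritation shares the same flow-chart row. The order is not stated, so it is worth stating, but the exposure is mainly at D90. Rounding down at both visits would also partly cancel in the change.
- **Every comparison is affected.** Nothing suggests that a scorer would prefer one nozzle over the other. If the between-product test on irritation means nozzle versus nozzle only, irritation is exposed mainly through the before/after change.

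The anchors are also firmer than a short quotation suggests. Irritation grade 1 is localised, whereas grade 2 may cover the whole treated area, and the obstruction grades describe how much of the membrane is visible. This narrows the room for judgement but does not close it.

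Finally, the supplied pages are the synopsis and flow-chart, with footers 11 to 13 of 64. A masking rule elsewhere in the plan cannot be excluded. If there is one, the synopsis should state it.

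**Conclusion.** The point holds for D90 scoring, on the pages supplied. The study is open, the control group uses no spray, both scores are clinician grades, and the scoring visit contains several tasks that reveal the group with no stated order. Spray versus control and the before/after change are exposed.

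The size is unknown. Under the central assumptions (SD 0.6, true increase 0.4 grade), average under-scoring of 0.1 or 0.2 grade cuts power to see harm from about 70% to 46% or 24%. Those figures require enough spray users at grade 1 or above for under-scoring to act on. This is a cheap improvement to a primary safety endpoint; it does not show that the result will be wrong.

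**What to change.** - **D0:** state that irritation and obstruction are both recorded before allocation is opened.
- **D90:** the ENT specialist scores and signs irritation and obstruction first, without access to allocation, product or log, and the subject is asked beforehand not to disclose the group. Product and log collection, questionnaire, adherence control and AE review follow.
- **Staff:** where site staffing allows, someone other than the scorer handles dispensing and collection. The supplied pages do not describe staffing, so this cannot be assumed; putting the scoring first works without it.
- **CRF:** add one line recording whether the score was made before the group was known.
- **Wording:** describe the design as open to subjects with masked scoring. If a site cannot do this, report the comparison as unmasked and list it as a limitation.

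The cost is tighter organisation within the two existing visits. No extra visit or assessor and no change to sample size or analysis is needed. Some unmasking will remain, through subjects or the scorer's memory of D0. Masking removes only the part of the bias that depends on the group: a drift common to all D90 scores would still affect the before/after change, and the control group's own change helps to show it.

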Exclusion criteria:	
 
1. Subjects who had surgical act on the mastoïde.
 
2. Subjects who had severe troubles of the internal ear (severe dizziness, desorientation, nausea).
 
3. Subjects using regularly a ear spray for washing his/her ears.
 
4. Subjects having a score of ear canal obstruction at 4 at D0.
 
5. Pregnant or nursing woman or planning a pregnancy during the study;
 
6. Subject who had been deprived of their freedom by administrative or legal decision or who is under guardianship;
 
7. Subject in a social or sanitary establishment;
 
8. Subject suspected to be non-compliant according to the investigator's judgment;
 
9. Subject with a condition or receiving a medication which, in the investigator's judgment, put the subject at undue risk;
 
10. Subject suffering from a severe or progressive disease.
 

Investigational device: Name / code	
OCEAN BIO-ACTIF Ear Hygiene (reverse nozzle)
 
OCEAN BIO-ACTIF Ear Hygiene (microdiffusion nozzle)
 
Bag on valve spray, with ergonomic nozzle

YSLAB	Medical Device CIP #23E1670	Final version 2.0 Date: 09/11/2023	Confidential Page 12/64
-------	--------------------------------	---------------------------------------	----------------------------

Galenic form	2 sprays in ear, every 3 days at home
Dosage	90 days
Duration	Topical to ear canal
Administration route	
Endpoints:	
Primary endpoints:
 
 
• Clinical evaluation,
 
• Clinical score of the irritation with structured scale,
 
• Record of the possible adverse reactions.
 
 
Secondary endpoints:
 
 
• Clinical score of the obstruction of ear canal,
 
• Results of audiogram with classification of the loss or win hearing function
 
• Subject satisfaction survey
 
• The number of auricular affection (such as otitis) during the use period
 

Study Procedures:	D0, D90

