	
(<math>\alpha=0.01</math>), in case of rejection, a Wilcoxon signed ranks test will be used.
 
To test whether the products differ statistically in terms of change from baseline (D90-D0), a two-sided t-test is used. If the normality assumption is not met, a non-parametric approach is used with a Wilcoxon signed rank test.
 
For the subjective evaluation questionnaire:
 
For each item of the subjective questionnaire, the raw data will be summarized in frequency (N) and percentage (%) by group of product.
 
All statistical tests will be assessed at <math>\alpha = 5\%</math> level of significance in a bilateral approach.
 
Statistical software: SAS® v9.4.

Foreseen study duration:	
Clinical investigation beginning: Q4 2023
 
Clinical investigation end: Q3 2024
 
Clinical investigation global duration: 8 months
 
Duration by subject: 90 days

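### Statistical methods do not name a spray-versus-control test for efficacy, and the within-product D90-D0 test cannot separate a spray effect from regression to the mean or natural change in wax

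*Combined protocol and SAP*

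**What the plan says.** All references are to the synopsis (section 1.5) unless noted.

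- **Entry.** Inclusion criterion 6: "Subjects having a clinical score of ear canal obstruction of 2 or 3 at D0". Exclusion criterion 4: "Subjects having a score of ear canal obstruction at 4 at D0". Inclusion criterion 4: "Subjects having history of cerumen occlusion more than once a year with or without symptoms".
- **Visits.** The flow-chart has D0 and D90 (±3 days) only, so the qualifying score is also the baseline.
- **Aims and design.** The secondary aims cover both nozzles and the control group, "in comparison to the baseline (D0) and between groups". The design is open, randomised and parallel-group, product versus control.
- **Sizes.** 33 subjects per nozzle with results, and "results on 24 subjects not using a spray (control group" as the third arm.
- **Methods for secondary endpoints.** First, "For each product, a paired t-test will be used to test whether the change from baseline (D90-D0) differ significantly from 0", with a signed-rank test if Shapiro-Wilk rejects at 0.01. Second, "To test whether the products differ statistically in terms of change from baseline (D90-D0"), by a two-sided t-test, again with a Wilcoxon signed-rank fallback.

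No sentence under Statistical methods mentions the control group, and none says which test decides efficacy.

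**The concern.** A subject chosen because the score stands at a given level on one day will, on average, drift towards his or her usual level by D90 without any treatment. Wax may also clear or build up over 90 days. A paired test against zero counts all of this as change under the spray. The control arm is there to remove it, but the second test refers to products, and the controls have none. Read literally, it compares the two nozzles with each other.

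A report could then follow the plan exactly and state that both nozzles improved significantly and did not differ, while the untreated arm improved just as much. If natural change is upward, the same test could hide a real benefit. With no deciding test named, the choice could also be made after the data are seen.

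**Working it through.** **1. The plan's own figures.** 72 + 27 = 99 included; 33 + 33 + 24 = 90 with results. The totals agree. No effect size, SD or power is given, so the size cannot be derived from a power calculation.

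**2. How little change the within-arm test needs.** With n = 33, the smallest significant mean change is t(0.975; 32)/√33 = 0.355 SD. Suppose an inert spray is accompanied by a natural mean change of 0.25 points with an assumed SD of 0.8. The noncentrality is (0.25/0.8)×√33 = 1.80 and the test is significant in 41% of trials. At 0.40 points it is 80%.

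**3. Regression to the mean alone, fixed score distributions.** All inputs here are assumptions: a latent normal score cut into five levels, no device effect, no trend, D0-D90 correlation 0.5 to 0.85, and subjects kept if the D0 score is 2 or 3. The t-test is applied to 33 subjects; the nominal rate of significant improvement is 2.5%.

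| Proportions at scores 0,1,2,3,4 | Mean | Significant improvement |
|---|---|---|
| .30,.30,.20,.12,.08; .20,.25,.25,.20,.10; .20 each | 1.38; 1.75; 2.00 | 9% to 70% |
| .10,.15,.25,.25,.25; .08,.12,.20,.30,.30 | 2.40; 2.62 | 2% to 5% |
| .05,.10,.20,.30,.35 | 2.80 | 1% or less; significant worsening about 6% to 7% |

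In the first row the mean change is -0.11 to -0.56 points, and the 24 untreated controls improve significantly in 7% to 53% of trials.

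**4. Adding natural change, second model.** Latent normal with SD 1, rounded to 0-4, using the plan's Shapiro-Wilk rule, 1000 runs per case. The no-trend column spans correlations 0.5 to 0.9; the other two use 0.7.

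| Latent mean | No trend | Natural loss 0.25 | Build-up 0.25 |
|---|---|---|---|
| 1.0 | 45-97% | 99.8% | 22% |
| 1.5 | 23-70% | 96% | 3% |
| 2.0 | 8-25% | 75% | 0.4% |
| 2.5 | 2-3% | 40% | 0% |
| 3.0 | about 0% | 12% | 0% |

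Entries are rates of significant improvement with an inert spray. At latent mean 3.0 with build-up, the inert arm worsens significantly in 73% of runs. The bias changes sign near 2.5, the midpoint of the entry window.

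**5. The randomised contrast.** In the same runs, a two-sample t-test or rank-sum test of 33 against 24 rejects in 3% to 6% in every case; the simulation standard error at 5% is √(0.05×0.95/1000) = 0.7 percentage points. Natural change is common to both arms and cancels.

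**6. Sensitivity of that contrast.** The difference detectable with 80% power at two-sided 5% is (1.960 + 0.842)×√(1/n₁ + 1/n₂):
- one nozzle versus control: 2.802×√(1/33 + 1/24) = 0.75 SD;
- pooled spray versus control: 2.802×√(1/66 + 1/24) = 0.67 SD;
- one nozzle versus control at 2.5%: (2.241 + 0.842)×0.268 = 0.83 SD.

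Power for 0.5 SD is 46% (33 versus 24) and 56% (66 versus 24).

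**7. The fallback.** A signed-rank test needs paired differences or a single sample. Subjects in different randomised arms are not paired, so it cannot compare 33 with 24. A five-level score makes it likely that the fallback would be called on.

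**The case against.** The comparison with control is planned: the secondary aims name all three groups and the design is randomised against control. Reading products to mean only the two nozzles would leave the control arm without a purpose. This stands, and a reader who infers that the trial means to judge efficacy by before-after change alone goes further than the documents. The gap is that the methods do not assign a test to a stated aim. Even on the charitable reading, the pairs to be tested and the deciding result are left open, and the fallback is unusable.

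A reader might also infer that subjects must on average improve. The documents do not support that. Score 4 is excluded, so selection is a window and its bias can vanish or reverse. Nor do they establish natural wax loss: recurrent occluders, including users of hearing aids, plugs or headsets, could as well build up wax.

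It is tempting to say that the paired test has the wrong false-positive rate. For its stated null of zero mean change, that has not been shown. The error lies in reading its result as a device effect, and no passage says that this will be done.

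Entry is not conditioned on hearing, so hearing is exposed only as far as it depends on wax. That was not computed.

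Finally, the available text is a synopsis and flow-chart from a longer plan. A fuller statistics section may name the contrast; if so, the synopsis should match it.

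**Conclusion.** The concern holds as a gap between aim and method. The control comparison is promised, the statistical text assigns no test to it, and the test that is spelled out cannot isolate a spray effect. The false-improvement rate for an inert spray could lie anywhere from about 0% to well above half, depending on a source distribution, a D0-D90 correlation and a natural trend that the documents do not give. All percentages rest on assumed latent-normal models and show what can happen, not what will. That the randomised contrast holds its level follows from randomisation and does not depend on those inputs. This should be fixed before analysis. It is not graver than that, because obstruction and hearing are secondary in a study whose principal aim is safety.

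**What to change.** In Statistical methods:

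1. State that efficacy on obstruction and hearing is concluded only from the randomised contrast with the control group (each nozzle versus control, or both nozzles pooled versus control), adjusted for the D0 score and reported with a 95% CI.
2. Reword the between-products sentence so that it tests whether each spray group differs from the control group, and the two nozzles from each other.
3. Replace the signed-rank fallback for between-group tests with a Wilcoxon rank-sum test or an ordinal model.
4. State how the two nozzle-versus-control comparisons are handled for multiplicity.
5. Keep within-group D90-D0 changes, control included, as descriptive estimates.
6. Say how controls who use the permitted prescribed ear drops enter the analysis, since that use may blur the contrast.

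This changes wording only and needs no new data. The cost is a wider interval and lower sensitivity. With an assumed SD of change of 0.8 points, the detectable differences are about 0.75×0.8 = 0.60 points for one nozzle versus control and 0.67×0.8 = 0.54 points pooled, so the efficacy result may look less favourable than a paired test would.

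### The primary irritation analysis tests signed change with no limit on D0 irritation, so healing of existing irritation can offset new irritation and make a non-significant result look reassuring

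*Combined protocol and SAP*

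**What the plan says.** All references are to section 1.5 (overall synopsis) and the flow chart, which are the parts available.

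- **Primary test.** Under Statistical methods, Primary endpoint: "For each product, a paired t-test will be used to test whether the change from baseline (D90-D0) differ significantly from 0". Normality is checked with Shapiro-Wilk at 0.01, and "in case of rejection, a Wilcoxon signed ranks test will be used".
- **Comparison.** A further sentence begins "To test whether the products differ statistically in terms of change from baseline (D90-D0), a" and goes on to a two-sided t-test with a non-parametric alternative. It does not say whether the control group is one of the things compared.
- **Scale.** Irritation is scored 0 to 3. The top grade is "3: severe irritation (serious erythema with potential oedema and/or scar").
- **Eligibility.** Two of the 16 criteria use a D0 score, and both concern obstruction, a secondary endpoint: inclusion 6, "Subjects having a clinical score of ear canal obstruction of 2 or 3 at D0", and exclusion 4, "Subjects having a score of ear canal obstruction at 4 at D0". None names irritation. The nearest is exclusion 9, "Subject with a condition or receiving a medication which, in the investigator's judgment, put the subject at undue risk", which sets no grade.
- **Other safety data.** The primary endpoints also include clinical evaluation and a record of adverse reactions. No test or threshold is given for either.
- **Data collected.** The flow chart has irritation scored at both D0 and D90.

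**The concern.** The principal aim is to confirm that the spray is safe. Under that aim a null result on irritation is the favourable result, so anything that pulls the test towards null works in the product's favour.

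A signed change does this whenever some subjects enter with irritation. If a subject enters at grade 1 or 2 and is better at D90, the negative change is set against the positive change of a subject who entered clear and became irritated. The t-test nets the two through the mean, and the signed-rank test nets them through the rank sums. Neither can tell a group in which nobody changed from one in which healing and new irritation were in balance. The synopsis plans no proportion worsening, no shift table, and no stratification or adjustment by D0 irritation that would show the difference.

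**Working it through.** **The plan's own figures.** The sample sizes add up: 72 + 27 = 99 included and 66 + 24 = 90 evaluable. No effect size, SD, power or safety margin is stated for irritation, so there is no power figure to reproduce.

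**Inputs from the synopsis.** 33 evaluable subjects per nozzle, 24 controls, scale 0 to 3, two-sided 5% level.

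**Assumed.** The numbers worsening and healing, because the documents give no D0 irritation distribution.

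**Step 1: which test applies.** With most changes at zero, Shapiro-Wilk gives p < 0.0001 in every example below, so the signed-rank fallback applies.

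**Step 2: one nozzle, 8 of 33 going up one grade.** When all non-zero changes are one grade, the exact signed-rank test equals the sign test. With w worsening, h healing and m = w + h, p = 2 × Σ C(m,k)/2^m over k from w to m.

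| Healers | Mean change | Exact signed-rank p | t-test p |
|---|---|---|---|
| 0 | 8/33 = +0.24 | 2 × 1/256 = 0.008 | 0.003 |
| 2, by one grade | 6/33 = +0.18 | 2 × (45+10+1)/1024 = 0.11 | 0.056 |
| 4, by one grade | 4/33 = +0.12 | 2 × (495+220+66+12+1)/4096 = 0.39 | 0.25 |
| 4, from grade 2 to 0 | (8−8)/33 = 0 | 0.84 | 1.00 |

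In the last row the eight +1 changes each have rank 4.5 and the four −2 changes each have rank 10.5. The rank sums are 8 × 4.5 = 36 and 4 × 10.5 = 42, and enumerating all sign patterns gives p = 0.84. The same 8 of 33 (24%) are newly irritated in every row. Two healers, 2/33 = 6% of the nozzle group, are enough to lose significance.

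**Step 3: how often harm is flagged.** This used 3,000 simulated trials per scenario. Assumptions: 25% risk of a one-grade worsening in users and none in controls; D0 irritation at grade 1; irritated subjects in either arm heal one grade with probability 0.5 to 0.8. The comparison column is a rank-sum test of 33 users against 24 controls, if one is done.

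| Irritated at D0 | Within-nozzle test | Against control |
|---|---|---|
| 0% | about 86% | about 94% |
| 10% | 34–50% | 61–70% |
| 20% | 7–23% | 44–55% |
| 30% | 2–9% | 37–45% |

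**Step 4: what control does in one example.** Take the last row of step 2 and suppose 3 of 24 controls also heal by two grades. The control mean is −6/24 = −0.25, so the user-minus-control difference is +0.25 rather than 0, and the rank-sum p is 0.075, against 0.84 within the nozzle. Control largely removes the directional error but leaves a loss of power.

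**Step 5: precision of a worsening proportion.** For 8/33 = 24%, the exact (Clopper-Pearson) limits are the 2.5% point of Beta(8, 26) and the 97.5% point of Beta(9, 25), giving 11% to 42%. Healers elsewhere in the group do not change this figure.

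**The case against.** The strongest reply is that the trial is randomised with a control group. Natural healing should occur there too, so in a between-arm contrast it balances on average. A reader might infer that healing would be credited to the spray throughout the analysis, but the documents do not support that: it holds for the within-product test only. What stands is that the within-product test comes first in the primary analysis, the comparison sentence speaks only of products, and steps 3 and 4 show lost power even if control is included.

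A reader might also infer that entry is wholly open and that harm in a grade 3 ear could not register at all. That goes too far. Exclusion 9 lets the investigator turn away some severe cases, and clinical evaluation and adverse reaction records could capture worsening that the score misses. A grade 3 entrant cannot score a positive change, but nothing says how many such subjects there would be, so the ceiling is a matter for separate reporting.

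Nor do the documents show that many subjects enter irritated. Inclusion 5, on users of ear devices, plugs or headsets aged 13 and over, says nothing about irritation. If nearly everyone enters at grade 0, the problem is negligible.

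Finally, the lack of a margin or acceptable irritation rate is a deeper weakness. That is fair, and it is a separate point which removing the netting would not settle.

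**Conclusion.** The point holds as a defect of analysis whose size is unknown. Healing offsets new irritation in the planned within-product test, and no criterion prevents subjects with D0 irritation from entering. With 8 of 33 users newly irritated, the signed-rank p runs from 0.008 with no healers to 0.84 with 4 healing from grade 2 to 0. These cases are constructed; with nobody irritated at D0 the effect is nil.

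The documents do not support a conclusion that the trial will be biased towards safety by a stated amount, or that entry must be restricted. A restriction to D0 grade 0, or a primary proportion limited to those subjects, would take aggravation of existing irritation out of the primary measure, and that is itself a safety question. The point merits a change because the correction uses data already collected and costs little.

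**What to change.** In Statistical methods, Primary endpoint:

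1. Define the primary irritation measure as the proportion of subjects whose score rises by at least one grade from D0. Report it per nozzle with an exact 95% confidence interval, and compare it with the control group, naming that group in the text.
2. Add a D0-by-D90 shift table by arm for all subjects, so that healing and worsening are both visible.
3. Count and report subjects entering at grade 3 separately. They cannot rise, so in the denominator they could only lower the proportion.
4. Keep the mean-change test as supportive. No entry restriction is needed.

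The objective asks for "scoring of the irritation of the ear canal at D60 in comparison with basal scoring of irritation at D0 (scale 0 to 3"), whereas the analysis and flow chart use D90. These passages must be reconciled so that the proportion has one defined time point.

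The cost is a change of analysis wording, with no new visits or data. The downsides are that dichotomising loses some information on the size of change, and the intervals are wide at n = 33. A subject whose old irritation heals and who is irritated anew to the same grade still shows no change; two scores alone cannot reveal that.
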